6.1.2 Radiation Therapy

- Start Date: All patients with remaining teeth will have a pre-radiotherapy dental evaluation. Feeding tube will be placed in patient at the discretion of the radiation oncologist and medical oncologist. Radiation therapy will begin on Day 1.
- Immobilization: Immobilization should include neck and shoulders utilizing the standard practice of Aquaplast mask.
- Treatment Planning CT: will be obtained with standard 0.3 cm slices through the regions that include the target volumes. PET/CT and/or MR scans may be used to assist in the definition of the target volumes, especially when the targets extend near the base of skull.

6.1.2.1 Target Volumes:

The treatment volume will include the gross tumor volume with an organ at risk (OAR) adapted margin of 0.1-1.5 cm to the planning target volume. Elective nodal coverage will not be included.

The definition of volumes will be in accordance with The International Commission on Radiation Units and Measurements (ICRU) Report # 50 and 62.

- Gross Tumor Volume (GTV) is the gross palpable or visible/demonstrable extent and location of the malignant growth. The GTV will be determined utilizing a combination of clinical examination (including endoscopy) and radiographic exams (utilizing CT, PET/CT or MRI).
- Clinical Target Volume (CTV) is a tissue volume that contains a demonstrable GTV and/or is considered to contain microscopic, subclinical extensions at a certain probability level. This volume thus has to be treated adequately in order to achieve the aim of

therapy. In the re-irradiation setting we will at most treat 1-2 nodal levels in addition to the gross tumor volume and the margin will be 3-5mm.

- Planning Target Volume (PTV) is a geometrical concept, and it is defined to select appropriate beam sizes and beam arrangements, taking into consideration the net effect of all the possible geometrical variations and inaccuracies in order to ensure that the prescribed dose is actually absorbed in the CTV. A minimum of 3-5 mm around the CTV will be utilized, excluding extension into the spinal cord and non-involved normal tissue.
- Spinal Cord: The spinal cord will be defined based upon CT scan. A spinal cord “planning” volume (PRV) also will be defined by adding a symmetrical margin of at least 0.5 cm in all dimensions around the cord.
- Mandible: The mandible includes the entire bony structure from TMJ through the symphysis.
- Brainstem: The brainstem will be defined based upon the CT scan. A brainstem “planning” volume (PRV) also will be defined by adding a symmetrical margin of at least 0.3 cm in all directions around the brainstem.
- Larynx: The larynx will be defined as the portion of the larynx from the top of the thyroid cartilage to the bottom of the cricoid cartilage that does not include any portion of the PTV. No additional margin will be added around the larynx.
- Brachial Plexus: defined per RTOG atlas (<https://www.rtog.org/CoreLab/ContouringAtlases.aspx>)
- Cervical Esophagus: This is defined as a tubular structure that starts at the bottom of pharynx and extends to the thoracic inlet.

6.1.2.2 Lymph Node Regions and Normal Tissues:

The lymph node groups at risk will be determined and their volumes (CTVs) will be outlined on the treatment planning CT according to image-based nodal classifications (RTOG online nodal atlas can be used as a reference; www.rtog.org). In the re-irradiation setting the patients will not receive elective nodal irradiation, however 1-2 lymph nodal levels may be added at the discretion of the radiation oncologist based on imaging and other clinical factors.

The normal tissue volumes to be contoured will include the brainstem, brain stem + 0.3 cm margin, spinal cord, spinal cord + 0.5 cm margin, mandible, larynx, parotid glands, cochlea, oral cavity, optic nerves, optic chiasm, globes, brachial plexus.

6.1.2.3 Dosimetric Planning:

Intensity Modulated Radiation Therapy (IMRT) and/or Volumetric Modulate Arc Therapy (VMAT) planning and delivery will be performed in all cases. The treatment plan used for each patient will be based on an analysis of the volumetric dose, including DVH analyses of the PTV and critical normal structures. The treatment aim will be the delivery of radiation to the PTVs and exclusion of noninvolved tissue as much as feasible.

6.1.2.4 Dose Specification:

The dose prescription is to be based on a dose distribution corrected for heterogeneities.

A list of the approved Treatment Planning Systems (TPS) and algorithm for dose calculation can be found on the IROC Houston web site.

The prescription dose will be normalized to the isodose which encompasses at least 95% of the planning target volume (PTV).

No more than 20% of the PTV will receive > 110% of its prescribed dose.

No more than 1% of any planning target volume will receive < 93% of its prescribed dose.

No more than 1% or 1 cc of tissue outside the PTV will receive > 110% of the dose prescribed to the PTV.

The dose prescription will be based on dose distribution corrected for tissue inhomogeneity.

PTV 60 Gy will include the primary tumor and involved nodal regions if adjacent nodal regions have disease or are at high risk. 1-2 levels of lymph nodal levels can be treated at the discretion of the radiation oncologist and based on imaging data (CT, PET/CT and/or MRI). The dose in this region can go as high as 66 Gy as long as the normal structure tolerances are met.

6.1.2.5 Suggested Dose restraints for critical normal structures

For CNS structures, Brainstem, Optic nerve and Optic chiasm: No more than 0.03 cc can exceed 60 Gy (from current AND previous radiation therapy treatments combined). Mandible: There are no specific requirements for brachial plexus dose, but if it is not grossly involved with or immediately adjacent to tumor, the dose should be kept as low as reasonably possible. Minimize hot spots.

Brachial plexus: There are no specific requirements for brachial plexus dose, but if it is not grossly involved with or immediately adjacent to tumor, the dose should be kept as low as reasonably possible. Minimize hot spots.

Larynx: There are no specific requirements for larynx dose, but if it is not grossly involved with or immediately adjacent to tumor, the dose should be kept as low as reasonably possible. Minimize hot spots.

6.1.2.6 Treatment Delivery/ Equipment:

Megavoltage equipment capable of delivering static-gantry intensity modulation beams with a multi-leaf collimator or dynamic intensity modulation (using a multi-leaf collimator or tomotherapy) is required. Other techniques are acceptable as long as dose specifications and constraints are satisfied. This includes tomotherapy and Volumetric Modulated Arc Therapy (VMAT) techniques. It is expected that the entire treatment of definitive irradiation will be completed in approximately seven weeks. Radiation course should be continuous (Monday-Friday) for 5 days. However, if an interruption is required for radiation reaction, it should be kept to a minimum, recorded, and justified.

6.2 Definition of Dose-Limiting Toxicity

Dose-limiting toxicity (DLT) will be defined as any one of the following adverse events, possibly attributable to the combination of birinapant and radiotherapy, that occur within 42 days of the start of therapy:

- Any grade 5 toxicities.

- Any grade ≥ 4 hematologic toxicity except for lymphopenia.
- Any grade ≥ 3 non-hematologic toxicity, **except for any of the following:**
 - nausea and vomiting that can be managed with standard supportive care over 2 weeks
 - alopecia,
 - drug-related fever,
 - radiation-induced in-field related side effects, including but not limited to dermatitis, oral mucositis and related pain, dysphagia, dysgeusia, esophagitis, xerostomia, weight loss, thickened oral secretions that can be managed with standard supportive care over 2 weeks
 - isolated laboratory abnormalities without clinical sequelae
- \geq grade 3 prolonged (> 7 days) serum amylase or lipase elevation*
- \geq grade 3 prolonged (> 7 days) aspartate aminotransferase (AST) elevation*
- \geq grade 3 prolonged (> 7 days) alanine aminotransferase (ALT) elevation*
- Concurrent elevation of AST/ALT > 3 times the upper limit of normal and bilirubin > 2 times the upper limit of normal (i.e., Hy's law)
- Any grade toxicity that mandates discontinuation of birinapant treatment for more than 2 weeks

* all of which will be considered to be dose limiting.

Grade 5 AEs are unacceptable, though the chances of their occurrence are considered to be quite low. The probability of DLTs with birinapant in combination with radiotherapy at the specified dose levels are expected not to exceed 30% of patients. All AEs \leq grade 4 are considered acceptable in terms of risk, given that the median overall survival of patients with locoregionally recurrent head and neck cancer who have received 1 or 2 lines of standard of care treatment is very short (approximately 3-6 months).

Criteria are based on the NCI Common Terminology Criteria for Adverse Events, Version 5.0.

Dose escalation will proceed within each dose level according to the following scheme. Dose-limiting toxicity (DLT) is defined above.

Number of Patients with DLT at a Given Dose Level	Escalation Decision Rule
0 out of 3	Enter 3 patients at the next dose level.
≥ 2	Dose escalation will be stopped. This dose level will be declared the maximally administered dose (highest dose administered). Three (3) additional patients will be entered at the next lowest dose level if only 3 patients were treated previously at that dose.
1 out of 3	Enter at least 3 more patients at this dose level. 
• If 0 of these 3 patients experience DLT, proceed to

	
the next dose level.
 
• If 1 or more of this group suffer DLT, then dose escalation is stopped, and this dose is declared the maximally administered dose. Three (3) additional patients will be entered at the next lowest dose level if only 3 patients were treated previously at that dose.
≤1 out of 6 at highest dose level below the maximally administered dose	This is generally the MTD. At least 6 patients must be entered at the MTD.

This dose escalation plan, on average, will select a maximum tolerated dose with the specified acceptable probabilities of DLT.

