6.5 Duration of Therapy

In the absence of treatment delays due to adverse event(s), treatment may continue for 2 cycles or until one of the following criteria applies:

- Disease progression
- Intercurrent illness that prevents further administration of treatment
- Unacceptable adverse event(s) as described in Sections [6.2](#) and [7](#).
- Patient decides to withdraw from the study
- General or specific changes in the patient's condition that render the patient unacceptable for further treatment in the judgment of the investigator

- Clinical progression
- Patient experiences a grade 4 non-hematologic toxicity or any grade 3 toxicity not returning to \leq grade 1 after 2 weeks of supportive care. The patient may continue with IMRRT but will be taken off birinapant.
- Patient non-compliance with <80% of birinapant doses (less than 3 out of the 4 total doses) or with scheduled appointments for investigational treatment that may affect treatment outcome, per PI discretion.
- Pregnancy
 - All women of child bearing potential will be instructed to contact the investigator immediately if they suspect they might be pregnant (e.g., missed or late menstrual period) at any time during study participation.
 - The investigator must immediately notify CTEP in the event of a confirmed pregnancy in a patient participating in the study.
- Termination of the study by sponsor
- The drug manufacturer can no longer provide the study agent

The reason(s) for protocol therapy discontinuation, the reason(s) for study removal, and the corresponding dates must be documented in the Case Report Form (CRF).

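### For certain grade 4 and persisting grade 3 events, the exemptions in 6.2 and its last bullet lead to different DLT classifications, and no precedence is stated

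*Combined protocol and SAP*

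**What the plan says.** Section 6.2 opens with "Dose-limiting toxicity (DLT) will be defined as any one of the following adverse events, possibly attributable to the combination of birinapant and radiotherapy", occurring within 42 days of starting therapy. Meeting a single bullet is therefore enough.

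The bullet on non-hematologic toxicity of grade 3 or higher applies "except for any of the following". Its exceptions include "radiation-induced in-field related side effects, including but not limited to dermatitis, oral mucositis and related pain", in a list ending with "thickened oral secretions that can be managed with standard supportive care over 2 weeks", and "isolated laboratory abnormalities without clinical sequelae". Neither has an upper grade limit, and the laboratory exception has no time limit. The hematologic bullet separately excepts lymphopenia. Prolonged amylase, lipase, AST and ALT elevations and Hy's law have bullets of their own. The last bullet is "Any grade toxicity that mandates discontinuation of birinapant treatment for more than 2 weeks", with no exceptions attached.

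Section 6.5 gives as a stopping trigger "Patient experiences a grade 4 non-hematologic toxicity or any grade 3 toxicity not returning to" grade 1 or lower after 2 weeks of supportive care, and continues: "The patient may continue with IMRRT but will be taken off birinapant". Section 7.1.2 repeats the rule. Neither sets in-field effects, laboratory findings or lymphopenia apart.

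**The concern.** The DLT count is the primary endpoint and drives every 3+3 decision. An exemption for expected re-irradiation effects and silent laboratory changes has a clear purpose: such events should not set the MTD. If the same events take the patient off birinapant, and coming off birinapant is itself a DLT, the exemption is empty for exactly those events.

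The error could run either way. Expected re-irradiation toxicity could hold the MTD down, or severe but manageable mucosal toxicity could go uncounted, although 2.4 names mucosal toxicity among the effects the combination might worsen. Two investigators could classify the same patient differently and both cite the protocol.

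**Working it through.** The plan gives no figure on this point, so the check is a mapping of events through the text, followed by an illustration.

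**Step 1. Each event through 6.2, then 6.5 and 7.1.2.**

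| Event | Exempt in 6.2? | Birinapant stop required? | Result |
|---|---|---|---|
| Exempt-type grade 3 event, at grade 1 or lower within 2 weeks | Yes | No | No conflict |
| Grade 4 in-field effect, manageable | Yes | Yes | Conflict |
| Grade 3 in-field effect, above grade 1 at 2 weeks | Only if *managed* does not mean *resolved* | Yes | Conflict on that reading; otherwise a DLT both ways |
| Isolated laboratory abnormality (not amylase, lipase, AST, ALT or Hy's law), grade 4, or grade 3 beyond 2 weeks | Yes | Yes | Conflict |
| Grade 3 lymphopenia beyond 2 weeks | Yes, under the hematologic bullet | Yes, as a grade 3 toxicity | Conflict |
| In-field effect of grade 3 or higher, not manageable | No | Not needed | DLT both ways |

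Manageable grade 4 vomiting lasting more than 24 hours follows the same path as the second row, because 7.1.5.2 also stops birinapant for it.

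**Step 2. What the alternative to a DLT is.** Four doses are planned. Section 6.1.1 requires 80% of the planned dose for DLT evaluability: 0.80 × 4 = 3.2 doses. Three of four is 75%, which fails on the arithmetic, although 6.5 treats only fewer than three of four as falling short. Section 9.2 asks for one dose only and replaces patients who are not evaluable. If the exemption prevails, the patient is therefore either a non-DLT or a replacement, depending on the section followed.

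**Step 3. Timing.** Doses fall on study days 2, 9, 21 + 2 = 23 and 21 + 9 = 30, while the 6.2 window is 42 days. After day 30 no scheduled dose remains to discontinue, so the last bullet may not be triggered. The same exempt-type event can be classified differently by onset date alone.

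**Step 4. Effect on the 3+3 table.** Take three patients with no other DLT. With no such event counted, the result is 0/3 and the trial escalates. Counting one gives 1/3, and three more patients are added. Counting two gives 2/3, and escalation stops. At the highest level 9.2 adds three patients after 0/3 as well, so there one event changes the count carried into six patients rather than the immediate action.

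**Step 5. Illustration.** Let p be the rate of undisputed DLTs and q the rate of disputed events. Both are assumed, taken as independent, and undisputed DLTs are taken to count whatever dose was received. The chance of passing one level at DLT rate r is (1−r)³ + 3r(1−r)² × (1−r)³, where:

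- not a DLT: r = p
- counted: r = 1 − (1−p)(1−q)
- replaced: r = p / [p + (1−p)(1−q)]

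For p = 10% and q = 20%, r is 0.10, 1 − 0.9 × 0.8 = 0.28, and 0.1/0.82 = 0.122.

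| q (p = 10%) | Not a DLT | Counted | Replaced |
|---|---|---|---|
| 5% | 0.906 | 0.824 | 0.898 |
| 10% | 0.906 | 0.730 | 0.889 |
| 20% | 0.906 | 0.536 | 0.868 |
| 30% | 0.906 | 0.360 | 0.840 |

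**The case against.** The strongest reply is that the text already gives an order. Any one bullet suffices, the exceptions are nested under particular bullets, and the last bullet stands alone. On that reading these events are DLTs and nothing is ambiguous. This stands as the literal reading. It does not show that the result was intended, since it cancels the exceptions for the events in question.

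Other parts of the reply also stand, and they narrow the point:

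- The in-field exception has its own manageability qualifier, so ordinary grade 3 events that recover in time raise no conflict.
- Section 7.1.4 softens the stop: asymptomatic grade 3 laboratory events resolving within 7 days need no modification, and birinapant may be reconsidered after grade 4 toxicity of under 24 hours. Section 7.2 lets radiation be held for grade 4 radiation toxicity, with birinapant held and restarted alongside it. These differ from 6.5 and 7.1.2, so they add to what must be reconciled.
- Whether a grade 4 laboratory abnormality can be free of sequelae depends on CTCAE text that the documents do not reproduce.
- Weekly team review, Medical Monitor approval between cohorts and at least monthly calls with the CTEP Medical Officer make an unnoticed misclassification less likely. They do not tell reviewers which rule applies.

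A reader might also quote stopping probabilities of 29%, 51% or 69%, which follow from the 3+3 formula at disputed-event rates of 20%, 30% or 40% with no other DLT (for 20%, 1 − 0.709 = 0.291). The arithmetic is right, but the rates are assumed and the replacement outcome is left out, so they are not estimates for this trial.

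**Conclusion.** The point holds for a defined set of events: those marked as conflicts in the table, with persisting grade 3 in-field effects included only if *managed* does not mean *resolved*. For these, the primary endpoint depends on a precedence that 6.2 does not state, and a single event in a cohort of three can change the decision. The pass probabilities show sensitivity only. In them, counting an event matters far more than choosing between a non-DLT and a replacement.

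Four stronger readings may suggest themselves, and the documents do not support them:

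- That every exempted event becomes a DLT. Events that recover in time do not.
- That, if the exemption prevails, grade 4 in-field toxicity never counts. Unmanageable in-field toxicity is still a DLT, and so is any grade 5 event.
- That after day 30 classification turns only on whether a dose remains. The other bullets still apply.
- That completed cohorts were misclassified. The amendment letter reports no DLTs requiring expansion of the first two cohorts, and does not say whether events of the disputed kind occurred.

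**What to change.** Reconcile 6.2, 6.5, 7.1.2, 7.1.4, 7.1.5.2 and 7.2 with one another, and 6.1.1 with 9.2 on evaluability. In 6.2:

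- State whether the last bullet applies to events excepted in the other bullets.
- State how an event arising after the final birinapant dose but inside the DLT window is classified.
- Give the manageability qualifier, including its 2-week period, a meaning consistent with 6.5 and 7.1.2.

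Apply the reconciled definition to the completed cohorts and to cohorts 3 and 4. This is best done before those cohorts are read, because the December 2022 amendment lets up to three patients enroll in each without staggered observation. Which grade, duration or stopping rule to adopt is the sponsor's clinical decision.

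The cost is protocol wording and a re-check of the few patients already treated. No patients or procedures are added.

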6.3 Dose Expansion Cohort

Birinapant will be administered IV over 30 minutes on days 2 and 9 of every cycle at the MTD estimated during dose escalation part of the study.

IMRRT will be administered starting on Day 1 at 2Gy/day x 5 days/week/M-F for 2 cycles (6 weeks) to a total of 60-66Gy.

IMRRT will start within 1-4h after the infusion of birinapant.

The study team will meet weekly to review the ongoing results of the trial and will continue to monitor and record AEs during the dose expansion portion of the study.

An expansion cohort of 10 additional patients will be treated at the MTD and the results combined with those of patients at the MTD to obtain improved estimates of safety and toxicity as well as to perform analyses to address secondary objectives.

6.4 General Concomitant Medication and Supportive Care Guidelines

Because there is a potential for interaction of birinapant with other concomitantly administered drugs, the case report form must capture the concurrent use of all other drugs, over-the-counter medications, or alternative therapies. The Principal Investigator should be alerted if the patient is taking any agent known to affect or with the potential for drug interactions. A Patient Drug Information Handout/Wallet Card is provided ([Appendix B](#)).

6.5 Duration of Therapy

In the absence of treatment delays due to adverse event(s), treatment may continue for 2 cycles or until one of the following criteria applies:

- Disease progression
- Intercurrent illness that prevents further administration of treatment
- Unacceptable adverse event(s) as described in Sections [6.2](#) and [7](#).
- Patient decides to withdraw from the study
- General or specific changes in the patient's condition that render the patient unacceptable for further treatment in the judgment of the investigator

- Clinical progression
- Patient experiences a grade 4 non-hematologic toxicity or any grade 3 toxicity not returning to \leq grade 1 after 2 weeks of supportive care. The patient may continue with IMRRT but will be taken off birinapant.
- Patient non-compliance with <80% of birinapant doses (less than 3 out of the 4 total doses) or with scheduled appointments for investigational treatment that may affect treatment outcome, per PI discretion.
- Pregnancy
 - All women of child bearing potential will be instructed to contact the investigator immediately if they suspect they might be pregnant (e.g., missed or late menstrual period) at any time during study participation.
 - The investigator must immediately notify CTEP in the event of a confirmed pregnancy in a patient participating in the study.
- Termination of the study by sponsor
- The drug manufacturer can no longer provide the study agent

The reason(s) for protocol therapy discontinuation, the reason(s) for study removal, and the corresponding dates must be documented in the Case Report Form (CRF).

6.6 Duration of Follow Up

Patients will be evaluated for safety with follow up visits approximately 14 (+ 7) days and 28 (+/- 7) days after completion of, or removal from treatment. Patients removed from treatment for unacceptable adverse event(s) will be followed until resolution or stabilization of the adverse event.

Patients will be evaluated at 3 (+/- 2 weeks), 6 (+/- 4 weeks), 9 (+/- 4 weeks), 12 (+/- 4 weeks), 18 (+/- 4 weeks) and 24 (+/- 4 weeks) months after completion of treatment for tumor evaluations. These visits will be stopped after confirmation of disease progression.

If patients are unable or unwilling to come to these visits, they will be contacted by phone or e-mail.

